7.2 EXCLUSION CRITERIA

Patients who have met all the above inclusion criteria listed in [Section 7.1](#) will be screened for the following exclusion criteria which are sorted and numbered in the following subsection.

7.2.1 Exclusion criteria related to study methodology

- E 01. Age of less than 8 or greater than 17 years at the time of signed informed consent.
- E 02. Calculated LDL-C <130 mg/dL (3.37 mmol/L) during the screening period, after patient has been on stable LMT for at least 4 weeks.
- E 03. Patient without a diagnosis of heFH by genotyping or clinical criteria.
- E 04. Patients aged of 8 to <10 years in whom other available interventions to lower LDL-C have been sufficient.
- E 05. Patients not on a stable dose of LMT (including statin, as applicable) for at least 4 weeks prior to the screening visit and from screening visit to Day 1.
- E 06. Daily dose of statin that is above the maximum recommended dose for pediatric patients as per the local prescribing label.
- E 07. Use of nutraceutical products or over the counter therapies that may affect lipids which have not been at a stable dose for at least 4 weeks prior to the screening visit.
- E 08. Patients not previously instructed on a cholesterol-lowering diet prior to the screening visit.
- E 09. Body weight <25 kg.
- E 10. Patients aged of 8 to 9 years not being at Tanner Stage 1 and patients aged of 10 to 17 years not being at least at Tanner Stage 2 in their development.
- E 11. Patients with secondary hyperlipidemia.
- E 12. Patients with diagnosis of homozygous familial hypercholesterolemia.
- E 13. Patient who has received lipid apheresis treatment within 2 months prior to the screening period, or has plans to receive it during the study.
- E 14. Known history of type 1 or type 2 diabetes mellitus.
- E 15. Known history of thyroid disease.
- E 16. Known history of hypertension.
- E 17. Fasting triglycerides >350 mg/dL (3.95 mmol/L) at the screening visit.
- E 18. Severe renal impairment (ie, eGFR <30 mL/min/1.73 m² at the screening visit).
- E 19. ALT or AST >2 xULN (1 repeat lab is allowed).
- E 20. CPK >3 xULN (1 repeat lab is allowed).

E 21. Patient/parents who withdraws consent during the screening period (patient who is not willing to continue or fails to return).

E 22. Conditions/situations or laboratory findings such as:

- Any clinically significant abnormality identified at the time of screening that in the judgment of the Investigator or any sub-Investigator would preclude safe completion of the study or constrain endpoints assessment such as major systemic diseases.
- Patients considered by the Investigator or any sub-Investigator as inappropriate for this study for any reason, eg,:
 - Those deemed unable to meet specific protocol requirements, such as scheduled visits,
 - Those deemed unable to administer or tolerate long-term injections as per the patient or the investigator,
 - Presence of any other conditions (eg, geographic, social....) actual or anticipated, that the Investigator feels would restrict or limit the patient's participation for the duration of the study,
 - Uncooperative or any condition that could make the patient potentially non-compliant to the study procedures.

E 23. Treatment with any investigational medicinal product (IMP) within 8 weeks or 5 half-lives prior to the screening period, whichever is longer.

Note: If half-life is not known, then 8 weeks should be applied for non-biological IMP and 6 months for biological IMP.

7.2.2 Exclusion criteria related to mandatory background therapies

E 24. All contraindications to the background statins or other LMTs (as applicable) warning/precaution of use (when appropriate) as displayed in the respective National Product Labeling.

7.2.3 Exclusion criteria related to the current knowledge of alirocumab

E 25. Hypersensitivity to alirocumab or to any of the ingredients of alirocumab injections.

E 26. Females who have experienced menarche or females of childbearing potential who are sexually active who are unwilling or unable to be tested for pregnancy.

E 27. Positive pregnancy test in females who have experienced menarche or females of childbearing potential who are sexually active.

E 28. Females who are breast-feeding.

E 29. Females of childbearing potential who are sexually active and not protected by highly effective contraceptive method(s) of birth control (as defined in the informed consent form and/or in a local protocol addendum) and/or who are unwilling or unable to be tested for pregnancy.

Note: Females of childbearing potential who are sexually active or females who have experienced menarche must have a confirmed negative pregnancy test at screening and other study visits. Females of childbearing potential who are sexually active must use an effective contraceptive method throughout the entire duration of the study treatment and for at least 10 weeks after the last injection. The applied methods of contraception have to meet the criteria for a highly effective method of birth control according to the "International Conference on Harmonisation of

Technical Requirements for Registration of Pharmaceuticals for Human Use. M3(R2): Guidance on nonclinical safety studies for the conduct of human clinical trials and marketing authorization for pharmaceuticals. ICH. 2009 Jun: 1-25." (24). See [Appendix G](#).

7.2.4 Additional exclusion criteria during or at the end of screening or run-in phase before inclusion

- E 30. Patient who has withdrawn consent before inclusion (starting from signed informed consent).
- E 31. Despite screening of the patient, inclusion is stopped at the study level.

7.3 EXCLUSION CRITERIA FOR THE OPEN-LABEL EXTENSION TREATMENT PERIOD

7.3.1 Exclusion criteria related to study methodology

- E 32. Significant protocol deviation in the main phase based on the Investigator judgment, such as non-compliance by the patient.
- E 33. Patient who experienced an adverse event leading to permanent discontinuation from the main open label dose finding treatment period.
- E 34. Patients having any new condition or worsening of existing condition which in the opinion of the Investigator would make the patient unsuitable for entry into the extension phase, or could interfere with the patient participating in or completing the study.

7.3.2 Exclusion criteria related to the current knowledge of alirocumab

- E 35. Hypersensitivity to alirocumab or to any of the ingredients of alirocumab injections.
- E 36. Positive pregnancy test at last visit of the main treatment period (Week 14 [Cohort 3]/ Week16 [Cohorts 1 & 2], Visit 8).
- E 37. Females who have experienced menarche or females of childbearing potential not willing to continue highly-effective method(s) of birth control (as defined in the informed consent form and/or in a local protocol addendum) and/or who are unwilling or unable to be tested for pregnancy.

8 STUDY TREATMENTS

8.1 INVESTIGATIONAL MEDICINAL PRODUCT(S)

For Cohorts 1 to 3, sterile alirocumab drug product will be supplied at a concentration of 150 mg/mL as 1.2 mL minimum extractable volume in a 3 mL vial filled with 1.9 mL solution for the main treatment period and in 3 mL vials (or in prefilled syringes if available) for patient included in the extension period.

A detailed manual for alirocumab solution preparation will be provided to the pharmacist (or equivalent) for individual dose preparation.

For Cohort 4, sterile alirocumab drug product will be supplied at a concentration of 150 mg/mL as 1 mL volume in a prefilled syringe (PFS).

Main treatment period (Open-Label, Repeated Dose-Finding, Sequential Group):

The different doses prepared according to the cohort and the body weight will be:

- For Cohort 1: 30 mg Q2W for BW <50 kg and 50 mg Q2W for BW \geq 50 kg.
- For Cohort 2: 40 mg Q2W for BW <50 kg and 75 mg Q2W for BW \geq 50 kg.
- For Cohort 3: 75 mg Q4W for BW <50 kg and 150 mg Q4W for BW \geq 50 kg.
- For Cohort 4: 150 mg Q4W for BW <50 kg and 300 mg Q4W for BW \geq 50 kg.

The body weight assessed at inclusion visit will be the reference for alirocumab solution preparation.

For Cohorts 1 & 2: The study treatment is a single SC injection of 0.5 mL for 30, 40, 50 or 75 mg dose of alirocumab (according to the cohort and the body weight) extracted from vials, administered every 2 weeks in the abdomen, thigh, or outer area of the upper arm.

For Cohort 3: The study treatment is a single SC injection of 1 mL for 75 or 150 mg dose of alirocumab (according to the body weight) extracted from vials, administered every 4 weeks in the abdomen, thigh, or outer area of the upper arm.

For Cohort 4, sterile alirocumab drug product will be supplied at a concentration of 150 mg/mL as 1 mL volume in a prefilled syringe (PFS).

For Cohort 4: The study treatment is a single SC injection of 1 mL for 150 mg dose of alirocumab and 2 injections of 1 mL containing 150 mg each to provide a total 300 mg (2 mL) of alirocumab through PFS administered every 4 weeks in the abdomen, thigh, or outer area of the arm.

Dosing for the main dose finding treatment period should ideally be administered Q2W SC or Q4W SC at approximately the same time of the day; however, it is acceptable to have a treatment window of \pm 3 days. The time of day is based on the patient's preference.

Open-label extension (OLE) treatment period:

For Cohorts 1 to 3, alirocumab injections may be prepared from vials by the pharmacist (or equivalent) or supplied as prefilled syringes (PFS) depending on availability and additional considerations.

If the PFS is available in the extension phase, then patients may either switch from alirocumab injections prepared from vials to PFS or directly initiate PFS (depending on patient's date of entry into the extension phase). After appropriate training, the parent/guardian or patient (if appropriate) will administer the PFS at home or another preferred location. In certain cases, alternative arrangements may be made for the administration of alirocumab with PFS.

If the PFS is not available in the extension phase for Cohorts 1 to 3, then alirocumab injections prepared from vials will be administered at the clinical site (by the site staff) or at the patient's home or another preferred location contingent upon alternative arrangements being made for such an administration.

The alirocumab dose/dose regimen received during the open-label dose finding treatment period of the main phase will be continued every 2 weeks or every 4 weeks during the OLE period, since [REDACTED].

However, once the final optimal doses for the Phase 3 study are selected, and if device is available, then these final optimal doses from the Q2W or Q4W regimen will be administered to all patients in Cohorts 1 to 3 during the OLE period, based on their body weight at the time of the dose change.

For Cohorts 1 & 2: The study treatment is a single SC injection of 0.5 mL for 30, 40, 50 or 75 mg dose of alirocumab (according to the last dose in each cohort and DMC recommendations) provided in a prefilled syringe or in a syringe (extracted from vial), administered every 2 weeks in the abdomen, thigh, or outer area of the upper arm. Study drug will be administered by SC injection Q2W, starting at Week 16 and continuing up to the last injection, 2 weeks before the end of the open-label extension period.

For Cohort 3: The study treatment is a single SC injection of 1 mL for 75 or 150 mg dose of alirocumab (according to the body weight, the last dose and DMC recommendations) provided in a prefilled syringe or in a syringe (extracted from vial), administered every 4 weeks in the abdomen, thigh, or outer area of the upper arm. Study drug will be administered by SC injection Q4W, starting at Week 14 and continuing up to the last injection, 4 weeks before the end of the open-label extension period.

For Cohort 4, sterile alirocumab drug product will be supplied at a concentration of 150 mg/mL as 1 mL volume in a prefilled syringe (PFS).

For Cohort 4: The study treatment is a single SC injection of 1 mL for 150 mg dose of alirocumab and 2 injections of 1 mL containing 150 mg each to provide a total 300 mg dose (2 mL) of alirocumab through PFS, administered every 4 weeks in the abdomen, thigh, or outer area of the upper arm. Study drug will be administered by SC injection Q4W, starting at Week 12 and continuing up to the last injection, 4 weeks before the end of the open-label extension period.

Dosing for the open-label extension treatment period should ideally be administered Q2W SC or Q4W SC at approximately the same time of the day; however, it is acceptable to have a treatment window of ± 3 days. The time of day is based on the patient's preference.

Alirocumab administration will continue until at least 10 weeks before the initiation of the pediatric Phase 3 study in the site where the patient is potentially participating or December 2018, whichever comes first.

In the event an injection is delayed by more than 7 days or is completely missed, the patient should return to the original schedule of study drug dosing without administering additional injections. If the delay is less than or equal to 7 days from the missed date, the patient should administer the delayed injection and then resume the original dosing schedule.

Detailed instructions for transport, storage, preparation, and administration of IMP will be provided by the site to the patient/caregiver.

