During the open-label extension period for Cohort 3, the first injection administration will start at Week14 after the last injection administration at Week 4 (ie, 10 weeks after the last administration of alirocumab). The treatment kit number will be provided by IRT according to the last dose administered in Cohort 3. The first injection of the extension period will be done at the site by the investigator staff. If the self-injections by patient or another designated person (such as parent, nurse, etc.) are decided during the extension period a training injection should be planned 4 weeks before the first self-injection, under direct site staff supervision.

During the open-label extension period for Cohort 4, the first injection administration will start at Week 12 at the end of the 12-week open-label dose finding. The treatment kit number will be provided by IRT according to the last dose administered in Cohort 4. The first injection of the extension period will be done at the site by the investigator staff. If the self-injections by patient or another designated person (such as parent, nurse, etc.) are decided during the extension period a

training injection should be planned 4 weeks before the first self-injection, under direct site staff supervision.

During the extension treatment period, IMP should ideally be administered every 2 weeks SC or every 4 weeks at approximately the same time of the day; however it is acceptable to have a window period of ± 3 days. The time of the day is based on visit's time or patient's preference in case of self-injections.

If by mistake or due to other circumstances an injection is delayed by more than 7 days or completely missed (for Cohorts 1 and 2) or by more than 14 days or completely missed (for Cohort 3 and Cohort 4), then the patient should return to the original schedule of study treatment administration without administering delayed injections. On the other hand, if the delay is less than or equal to 7 days (for Cohorts 1 and 2) from the missed date or if the delay is less than or equal to 14 days for (Cohort 3 and Cohort 4) from the missed date, then the patient should administer the delayed injection and then resume the original schedule of study treatment administration.

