9.2.3.2 Adverse event

All AEs reported by the Investigator, will be described.

All AEs will be coded to a “Lowest Level Term”, “Preferred Term (PT)”, “High Level term (HLT)”, “High Level Group Term (HLGT)” and associated primary “System Organ Class (SOC)” using the version of MedDRA (Medical Dictionary for Regulatory Activities) currently in effect at Sanofi at the time of the considered database lock.

Groupings of AEs may include the following:

- General allergic events (AESIs or not, see [Section 10.4.1.3](#)).
- Local injection site reactions deemed to be allergic (AESIs or not, see [Section 10.4.1.3](#)).
- Neurologic adverse events (AESIs or not, see [Section 10.4.1.3](#)).
- Neurocognitive events.
- Symptomatic overdose with IMP:
 - An overdose (accidental or intentional) is an event suspected by the Investigator or spontaneously notified by the patient (not based on systematic injection counts) and defined as at least twice of the intended dose within the intended therapeutic interval (ie, 2 or more injections from the treatment kit are administered in <7 calendar days for patients in the Q2 week regimen and <14 calendar days for patients in the Q4 week regimen, or twice the planned dose at one injection due to IMP preparation error), to be reported using the corresponding screens in the eCRF using the term “symptomatic overdose (accidental or intentional)”. The patient should be monitored and appropriate symptomatic treatment instituted,
- Pregnancy of female patient (including male patient’s partner).
- ALT increase.

Adverse event observation period:

- The AE observations are per the observation periods defined above.

Death observation period:

- The death observations are per the observation period defined above. In addition, “post-study” death includes all deaths reported after the end of the study (see definition of end of study period per patient in [Section 6.2.2](#)).

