 - An overdose (accidental or [intentional]) is an event suspected by the Investigator or spontaneously notified by the patient (not based on systematic injection counts) and defined as at least twice of the intended dose within the intended therapeutic interval (ie, 2 or more injections from the treatment kit are administered in <7 calendar days for Q2W regimen or 2 or more injections from the treatment kit are administered in <14 calendar days for Q4W regimen) to be reported using the corresponding screens in the eCRF using the term "symptomatic overdose (accidental [or intentional])". The patient should be monitored and appropriate symptomatic treatment instituted if needed,

- The circumstances of the overdose should be clearly specified in the verbatim,
- Neurologic Events:
 - Neurologic Events that require additional examinations/procedures and/or referral to a specialist should be reported as an AESI. If the event does not require additional examinations/ procedures and/or referral to a specialist, it should be reported as a standard AE.
- Neurocognitive events:
 - All neurocognitive events will be considered as AESI.

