2.1.4 Safety endpoints

The safety analyses will be based on the reported adverse events (AEs) and other safety information, such as clinical laboratory data, vital signs, and tanner stage assessment.

Observation period

The period of safety observation starts from the time when the patient gives informed consent and is divided into the following periods:

- The PRE-TREATMENT period: defined as the time from the signed informed consent up to the first dose of IMP injection in the study;
- The OLDFI treatment-emergent adverse event (TEAE) period: defined as the time from the first OLDFI IMP injection up to the day of last OLDFI IMP injection + 70 days (10 weeks) as residual effect of alirocumab is expected until 10 weeks after discontinuation. For patients entering in the OLE, the OLDFI TEAE period will be truncated at the day before the first OLE IMP injection in the extension period;

The OLDFI TEAE period will include:

- The OLDFI TREATMENT period: defined as the time from the first OLDFI IMP injection up to the day of last OLDFI IMP injection + 21 days (for Cohorts 1 & 2) or + 35 days (for Cohort 3 & 4) . For patients entering in the OLE, the OLDFI treatment period will truncated at the day before the first OLE IMP injection in the extension period
- The OLDFI POST-TREATMENT period defined as the time starting the day after the end of OLDFI TEAE period. For patients entering in the OLE, the OLDFI POST-TREATMENT period will be truncated at the day before the first OLE IMP injection in the extension period;
- The OLDFI/OLE combined TEAE period: defined as the time from the first OLDFI IMP injection up to the day of last OLE IMP injection (or to last OLDFI IMP injection for patients not entering into the extension phase) + 70 days ;

The OLDFI/OLE combined TEAE period will include:

- The OLDFI/OLE combined TREATMENT period defined as the time from the first OLDFI IMP injection up to the day of last OLE IMP injection (or to last OLDFI IMP injection for patients not entering into the extension phase) + 21 days (for Cohorts 1 to 2) or + 35 days (for Cohorts 3 & 4). For patients from Cohort 3 who switched to selected Phase 3 doses, the OLDFI/OLE combined TREATMENT period is defined as

the time from the first OLDFI IMP injection up to the day of last OLE IMP injection
+ 21 days.

- The OLDFI/OLE combined POST-TREATMENT period defined as the time starting the day after the end of the OLDFI/OLE combined TEAE period.

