2.4.3.1 Extent of investigational medicinal product exposure

The total exposure to IMP will be assessed using the following parameters:

- Duration of OLDFI IMP injection exposure in weeks defined as (date of last OLDFI IMP injection – date of first OLDFI IMP injection + 14 days)/7 (for Cohorts 1& 2) or (date of last OLDFI IMP injection – date of first OLDFI IMP injection + 28 days)/7 (for Cohorts 3 & 4), regardless of unplanned intermittent discontinuations.
- The total number of OLDFI IMP injections by patient.
- For Cohorts 1 to 3, and for the OLDFI/OLE combined period the following parameters will be derived up to, and post switch of dose:
 - Duration of OLDFI/OLE combined period IMP injection exposure up to the switch to Phase 3 doses in weeks, defined as (date of last IMP injection up to the switch – date of first IMP injection + 14 days)/7 (for Cohorts 1& 2) or (date of last IMP injection up to the switch – date of first IMP injection + 28 days)/7 (for Cohorts 3 & 4), regardless of unplanned intermittent discontinuations.
 - Duration of IMP injection exposure post switch in weeks, defined as: (date of last IMP injection +14 – date of first IMP injection post switch)/7, regardless of intermittent discontinuations.
 - Total number of OLDFI/OLE combined period IMP injections up to, and post switch of dose.
- For Cohort 4, and for the OLDFI/OLE combined period, the following parameters will be derived:
 - Duration of OLDFI/OLE combined period IMP injection exposure in weeks, defined as (date of last IMP injection – date of first IMP injection + 28 days)/7, regardless of unplanned intermittent discontinuations.
 - Total number of OLDFI/OLE combined period IMP injections.
- For duration of IMP injection exposure calculation, see [Section 2.5.3](#) for calculation in case of missing or incomplete data. Non-integer values will be rounded to one decimal place.

Duration of OLDFI IMP exposure will be summarized descriptively as a quantitative variable (number, mean, SD, median, minimum, and maximum) and categorically using the following categories: ≥ 1 day to <1 week, ≥ 1 to <3 weeks, ≥ 3 to <5 weeks, ≥ 5 to <7 weeks, ≥ 7 to <9 weeks, ≥ 9 to <11 weeks, ≥ 11 weeks.

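### In the extension, a four-weekly dose 8 to 14 days late is skipped under Protocol Section 8.1 but given under Section 8.1.2; the limit should follow the current regimen

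*Protocol*

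**What the plan says.** Section 8.1 of the protocol, in its part on the open-label extension, describes Q2W dosing for Cohorts 1 and 2 and Q4W dosing for Cohorts 3 and 4. It then gives one late-dose rule for all of them: "In the event an injection is delayed by more than 7 days or is completely missed, the patient should return to the original schedule". A delay of 7 days or less means that the injection is given.

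Section 8.1.2 follows its own paragraph on extension dosing with a rule split by cohort. Cohorts 1 and 2 have the same 7-day limit. For the other two cohorts the dose is skipped only when late "by more than 14 days or completely missed (for Cohort 3 and Cohort 4"), and it is given "if the delay is less than or equal to 14 days for (Cohort 3 and Cohort 4) from the missed date".

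Two other parts of the plan bear on the rule:

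- **Overdose.** Section 9.2.3.2 sets the interval at "<14 calendar days for patients in the Q4 week regimen", and Section 10.4.1.3 repeats it: "2 or more injections from the treatment kit are administered in <14 calendar days for Q4W regimen". The Q2W limit in both places is <7 calendar days.
- **Switch of dose.** Once Phase 3 doses are chosen and the device is available, Section 8.1 says "these final optimal doses from the Q2W or Q4W regimen will be administered to all patients in Cohorts 1 to 3". Cohort 4 stays on its main-phase dose.

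**The concern.** A site with a Q4W injection 8 to 14 days late cannot comply with both sections, and nothing in the protocol says which prevails. These are working dosing instructions for children, some of which may be followed by families at home. The choice decides whether the child goes eight weeks without drug.

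The second weakness is that Section 8.1.2 attaches its limit to the cohort of enrolment. A Cohort 3 patient who leaves Q4W dosing would keep the 14-day allowance, although 14 days is a full Q2W interval. Copying the Section 8.1.2 rule into Section 8.1 would remove the contradiction but keep this problem.

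**Working it through.** The plan gives no figure of its own to reproduce. The check compares the two rules and counts days.

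**Inputs.** Intervals are 28 days (Q4W) and 14 days (Q2W). Skip thresholds are >7 days (Section 8.1, all cohorts), and >7 days (Cohorts 1 and 2) or >14 days (Cohorts 3 and 4) in Section 8.1.2. Overdose intervals are <7 days (Q2W) and <14 days (Q4W), from Sections 9.2.3.2 and 10.4.1.3. Let d be the delay in days, with the previous and next doses on their nominal dates.

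**Step 1: Q4W dosing.**

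| Delay d | Section 8.1 | Section 8.1.2 (Cohorts 3, 4) |
|---|---|---|
| up to 7 | give | give |
| 8 to 14 | skip | give |
| more than 14 | skip | skip |

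For d = 8 to 14:

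- Skipped: 2 × 28 = 56 days between doses.
- Given: 28 + d = 36 to 42 days since the previous dose, then 28 − d = 20 to 14 days to the next. This is never below 14, so it is not inside the Q4W overdose interval.

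For Cohorts 1 and 2 on Q2W the two sections agree at every delay.

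**Step 2: Cohort 3 after a switch to Q2W.** Under the Section 8.1.2 wording, a dose with d = 8 to 14 is still given. The next nominal dose follows in 14 − d = 6 to 0 days, always below 7 and so inside the Q2W overdose interval.

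The evidence that the switch would be to Q2W is indirect. SAP Section 2.1.4 says "For patients from Cohort 3 who switched to selected Phase 3 doses, the OLDFI/OLE combined TREATMENT period is defined as" running to 21 days after the last extension injection; the Q4W convention there is 35 days. SAP Section 2.4.3.1 has "Duration of IMP injection exposure post switch in weeks, defined as: (date of last IMP injection +14", where the Q4W convention is 28 days.

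**Step 3: limits set by regimen.** At the largest delay allowed, Q2W leaves 14 − 7 = 7 days and Q4W leaves 28 − 14 = 14 days. Each stays just outside its overdose interval.

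This holds on nominal dates. If the next dose were also brought forward by the permitted 3 days, the Q4W gap would be 25 − d, below 14 for d = 12 to 14. The Q2W gap would be 11 − d, below 7 for d = 5 to 7. The existing Q2W rule already carries that same edge.

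**Step 4: effect on a summary.** Take a Cohort 4 Week 20 dose that is 8 to 14 days late, with Weeks 16 and 24 on time. The Week 24 lipid sample, drawn before dosing, falls 56 days after the last dose under Section 8.1, or 20 to 14 days after it under Section 8.1.2. Both values could enter the same by-time-point extension summary (SAP Section 2.4.4.2.4).

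**The case against.** The best defence is that Section 8.1.2 is the section on timing and sets its limits by cohort, so most readers would follow it over the general sentence in Section 8.1. That is a likely reading, but the protocol does not state it, and Section 8.1 places its sentence straight after text covering both Q2W and Q4W extension dosing. The 14-day paragraph does not repeat that it concerns the extension. It does, however, follow extension text and carries no period limit.

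It is also fair to say that the effect is small. Extension lipids are summarised only descriptively, and the Section 8.1 rule sits under the extension heading, so the main-phase endpoints are out of reach. The Q2W switch for Cohort 3 is an inference, because Section 8.1 leaves the regimen open. All of this stands, and it limits the size of the point without removing the contradiction.

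A reader might go further on place of dosing. Footnote d to the Cohort 4 extension chart (Section 1.4.2) has site staff inject at the clinic. Section 8.1.2 plans for self-injection in Cohort 4, and Section 10.1.4.1 names Cohort 4 among those who may be dosed at home. One might infer that footnote d is a lone slip to be overruled. The documents do not support that:

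- The synopsis, Section 6.1 and Section 8.1 place home use of prefilled syringes under Cohorts 1 to 3.
- The Cohort 4 chart has no injection-training or kit-dispensation row, unlike the Cohorts 1 to 3 chart.
- Sections 10.1.4.1 and 10.1.4.4 confine diary text to Cohorts 1 to 3, although the Cohort 4 chart does carry diary and compliance rows.
- The phone call at Weeks 16 and 20 is only an option, so a site injection remains possible there.

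The text is mixed, and the choice belongs to the sponsor.

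A reader might also want to strike the reference to administration from the Cohort 4 bullets in Sections 10.1.4.4 and 10.1.4.5, since they appear to count kit allocations. That would remove the only Cohort 4 injection instruction in those visit lists, so it should stay.

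**Conclusion.** The late-dose contradiction is real and should be corrected. For Q4W delays of 8 to 14 days, the sections lead to a 56-day gap or to a gap of 36 to 42 days. It concerns Cohort 4, and Cohort 3 while on Q4W: about 10 patients in each, fewer to the extent that patients decline the optional extension. The documents do not allow an estimate of how many doses would be this late.

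A reader might infer that giving the late Q4W dose risks an overdose. On nominal dates it does not. The overlap arises only for a Cohort 3 patient on Q2W, and that rests on the switch being to Q2W. Even then the interval alone does not make a reportable event: the definition is not based on systematic injection counts, and the event of special interest is symptomatic overdose.

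The Week 8 primary endpoint and the Cohort 4 Week 12 endpoint are unaffected. The place-of-dosing inconsistency is also real, but it supports a question and not a prescribed change.

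**What to change.** In both Section 8.1 and Section 8.1.2, state the late-dose limit by the regimen that the patient is on at the time:

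- **Q2W** (Cohorts 1 and 2, and any Cohort 3 patient switched to Q2W): give if 7 days late or less, otherwise skip.
- **Q4W** (Cohort 4, and Cohort 3 while on Q4W): give if 14 days late or less, otherwise skip.

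In either case the patient then resumes the original schedule. The cost is rewording the late-dose sentences in two sections. No SAP change, visit or assessment is added.

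Separately, ask the sponsor whether Cohort 4 extension injections are to be given only at the clinic by site staff or also at home, and align the text with the answer. Clinic only means restricting Sections 8.1.1, 8.1.2 and 10.1.4.1 for Cohort 4. Home dosing means amending footnote d, adding training and dispensation rows to the Cohort 4 chart, and extending the diary text in Sections 10.1.4.1 and 10.1.4.4. That second route is more than a wording change.
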